### **13.3. Methods for Evaluation of Measurable Disease**

All measurements should be taken and recorded in metric notation using a ruler or calipers. All baseline evaluations should be performed as closely as possible to the beginning of treatment and never more than 4 weeks before the beginning of the treatment.

The same method of assessment, i.e. CT or MRI, and the same technique should be used to characterize each identified and reported lesion at baseline and during follow-up.

**Conventional CT and MRI:** This guideline has defined measurability of lesions on CT scan based on the assumption that CT slice thickness is 5 mm or less. If CT scans have slice thickness greater than 5 mm, the minimum size for a measurable lesion should be twice the slice thickness. MRI is also acceptable in certain situations (e.g., for body scans).

Use of MRI remains a complex issue. MRI has excellent contrast, spatial, and temporal resolution; however, there are many image acquisition variables involved in MRI, which greatly impact image quality, lesion conspicuity, and measurement. Furthermore, the availability of MRI is variable globally. As with CT, if an MRI is performed, the technical specifications of the scanning sequences used should be optimized for the evaluation of the type and site of disease. Furthermore, as with CT, the modality used at follow-up should be the same as was used at baseline and the lesions should be measured/assessed on the same pulse sequence. It is beyond the scope of the RECIST guidelines to prescribe specific MRI pulse sequence parameters for all scanners, body parts, and diseases. Ideally, the same type of scanner should be used and the image acquisition protocol should be followed as closely as possible to prior scans. Body scans should be performed with breath-hold scanning techniques, if possible.

**Tumor markers:** Tumor markers alone cannot be used to assess response. If markers are initially above the upper normal limit, they must normalize for a patient to be considered in complete clinical response.

### **13.4. Response Criteria- RECIST Criteria**

#### **13.4.1 Evaluation of Target Lesions**

Complete Response (CR): Disappearance of all target lesions. Any pathological lymph nodes (whether target or non-target) must have reduction in short axis to <10 mm.

Partial Response (PR): At least a 30% decrease in the sum of the diameters of target lesions, taking as reference the baseline sum diameters.

Progressive Disease (PD): At least a 20% increase in the sum of the diameters of target lesions, taking as reference the smallest sum on study (this includes the baseline sum if that is the smallest on study). In addition to the relative increase of 20%, the sum must also demonstrate an absolute increase of at least 5 mm. (Note: the appearance of one or more new lesions is also considered progressions).

Stable Disease (SD): Neither sufficient shrinkage to qualify for PR nor sufficient increase to qualify for PD, taking as reference the smallest sum diameters while on study.

#### **13.4.2 Evaluation of Non-Target Lesions**

Complete Response (CR): Disappearance of all non-target lesions and normalization of tumor marker level. All lymph nodes must be non-pathological in size (<10 mm short axis).

Note: If tumor markers are initially above the upper normal limit, they must normalize for a patient to be considered in complete clinical response.

Non-CR/Non-PD: Persistence of one or more non-target lesion(s) and/or maintenance of tumor marker level above the normal limits.

Progressive Disease (PD): Appearance of one or more new lesions and/or unequivocal progression of existing non-target lesions. Unequivocal progression should not normally trump target lesion status. It must be representative of overall disease status change, not a single lesion increase. Although a clear progression of “non-target” lesions only is exceptional, the opinion of the treating physician should prevail in such circumstances, and the progression status should be confirmed at a later time by the review panel (or Principal Investigator).

#### **13.4.3 Evaluation of Best Overall Response**

The best overall response is the best response recorded from the start of the treatment until disease progression/recurrence (taking as reference for progressive disease the smallest measurements recorded since the treatment started). The patient's best response assignment will depend on the achievement of both measurement and confirmation criteria.

**Table 9      Disease Assessment For Patients with Measurable Disease**

Target Lesions	Non-Target Lesions	New Lesions	Overall Response	Best Overall Response when Confirmation is Required*
CR	CR	No	CR	$\geq 4$ wks. Confirmation**
CR	Non-CR/Non-PD	No	PR	$\geq 4$ wks. Confirmation**
CR	Not evaluated	No	PR	
PR	Non-CR/Non-PD/not evaluated	No	PR	
SD	Non-CR/Non-PD/not evaluated	No	SD	documented at least once $\geq 4$ wks. from baseline**
PD	Any	Yes or No	PD	no prior SD, PR or CR
Any	PD***	Yes or No	PD	
Any	Any	Yes	PD	

\* See RECIST 1.1 manuscript for further details on what is evidence of a new lesion.  
 \*\* Only for non-randomized trials with response as primary endpoint.  
 \*\*\* In exceptional circumstances, unequivocal progression in non-target lesions may be accepted as disease progression.

**Note:** Patients with a global deterioration of health status requiring discontinuation of treatment without objective evidence of disease progression at that time should be reported as “symptomatic deterioration.” Every effort should be made to document the objective progression even after discontinuation of treatment.

### 13.5. Assessment of Disease According to Immune Related RECIST for Solid Tumors

Although this will not be the primary endpoint we will allow subjects to remain on study if they meet the criteria for immune related RECIST as described. The immune related RECIST (irRECIST), is adapted to account for the unique tumor response seen with immunotherapies.

The irRECIST criteria considers index lesions identified at baseline together with new lesions that may occur after the start of treatment and are incorporated into the calculated tumor burden. The appearance of new lesions alone does not constitute PD.

If imaging shows PD, tumor assessment should be repeated 4 weeks later to confirm PD with the option of continuing treatment for clinically stable subjects. Clinically stable will be defined by the following criteria:

- Absence of signs and symptoms indicating disease progression
- No decline in ECOG performance status

- Absence of rapid progression of disease
- Absence of progressive tumor at critical anatomical sites (eg, cord compression) requiring urgent alternative medical intervention
- Absence of disease progression in close proximity to a vital organ.

Subjects must meet the above bulleted criteria for clinically stable disease in order to continue on study treatment beyond initial imaging showing PD. Clinically stable subjects who continue on study treatment will first be reconsented.

In determining whether the tumor burden has increased or decreased, investigators should consider all target lesions as well as non-target lesions. Subjects who are deemed clinically unstable are not required to have repeat imaging for confirmation. If radiologic progression is confirmed, then the subject will be discontinued from study treatment as specified in the Protocol, and the first radiographic evidence of PD should be the date of progression. If radiologic progression is not confirmed, then the subject should resume/ continue study treatment and have their next scan according to the Protocol-specified schedule (ie 4 weeks later and then every 8 weeks). If progression is not confirmed and the subject continues on treatment, the next scan that documents disease progression (and is confirmed by a second scan at least 4 weeks later) will be considered the date of disease progression.

NOTE: If a subject with confirmed radiographic progression (ie, 2 scans at least 28 days apart demonstrating PD) is clinically stable or clinically improved, and there is no further increase in the tumor dimensions at the confirmatory scan, an exception may be considered to continue treatment upon consultation with the sponsor. In order for a patient to be considered clinically stable, all bulleted criteria listed above in section 13.5 must be fulfilled. Clinically stable subjects should also have at the confirmatory scan no further increase in the target lesions, no unequivocal increase in non-target lesions, and no additional new lesions develop (non-worsening PD) to continue study treatment. Such exceptions will need to be made in consultation with the study Sponsor and the trial's DSMC. However, study treatment continued beyond PD will be discontinued if radiologic progression worsens.

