### 1.1. Trial Design Overview

This is a single-arm, single-center, open-label trial of azacitidine combined with pembrolizumab in subjects with locally-advanced or metastatic pancreatic adenocarcinoma. Thirty-one evaluable subjects will be enrolled to assess the efficacy and safety of combination therapy in the second- line setting.

All subjects will have received systemic first-line chemotherapy, 5-FU or gemcitabine-based combination or monotherapy, prior to enrollment on the study. Azacitidine daily for 5 days will be given every 4 weeks (28 days). Fixed-dose pembrolizumab will be administered every 3 weeks for up to approximately 2 years beginning 2 weeks after initiation of azacitidine. The primary efficacy endpoint will be progression-free survival among all enrolled subjects. Disease progression will be determined based on RECIST 1.1 criteria; however, patients will be permitted to continue therapy following the development of progression of disease by RECIST 1.1 criteria if considered clinically appropriate by the study principal investigator.

As preliminary data suggests there is minimal toxicity overlap between pembrolizumab and a hypomethylating agent, there will be an accelerated Phase 1 dose determination component of the study. In the initial cohort, low-dose azacitidine will be administered, as studied in patients with advanced or metastatic solid tumors, and pembrolizumab will be administered at fixed dose

as detailed in the protocol. An initial cohort of 6 subjects will be enrolled, treated with combination therapy, and assessed for safety. Following enrollment of the initial 6 evaluable subjects all toxicity data will be reviewed. If 2 or more patients experience a treatment related dose-limiting toxicity (DLT) within the first 6 weeks of treatment administration (Defined in Section 5.2), then accrual at that dose level will stop. We will allow for 1 dose reduction in azacitidine and if agreed by the PI, the study will resume at the lower dose (Dose -1) and will again accrue 6 subjects who will receive combination therapy. If 2 or more subjects experience treatment related DLTs at this level, we will discontinue the combination study.

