## 5. STUDY DESIGN

### 5.1. General Design

This is a single-arm, open-label, single site Phase II trial of azacitidine combined with pembrolizumab in previously systemically treated subjects with a histologically or cytologically confirmed diagnosis of pancreatic ductal adenocarcinoma. Pre-treatment biopsies will be required for those subjects without an archival sample. All subjects will be required to provide a tumor tissue sample, either from the primary or a metastatic site, for biomarker analysis after 8 weeks on treatment. Thirty-one evaluable subjects will be allocated to receive azacitidine 50 mg/m^2 SubQ for 5 days every 28 days (Q4W) with single-agent pembrolizumab 200 mg IV every 3 weeks (Q3W) beginning on week 3.

The primary objective of this trial is to determine the PFS of pembrolizumab given in combination with a hypomethylating agent. Beginning with screening, all imaging assessments will be evaluated using RECIST 1.1. On-study imaging assessments will be performed every 8

weeks (Q8W) calculated from the date of allocation and independent of treatment delays. RECIST 1.1 will be used by the site for treatment decisions until the first radiologic evidence of progressive disease (PD).

Following the first radiologic evidence of PD by RECIST 1.1, treatment decisions may be made by the adaptation of RECIST 1.1 as described in [Section 13.5](#) termed immune-related RECIST (irRECIST) to accommodate the tumor response patterns seen with pembrolizumab treatment (e.g., tumor flare). This was first described by Nishino, et al. 2013 and is further modified for the pembrolizumab program as described in [Section 13.5](#). For a clinically stable subject with first radiologic evidence of PD, it is at the discretion of the principal investigator to continue treating the subject with pembrolizumab until PD is confirmed at least 4 weeks after the date of the first tumor imaging confirming PD per the principal investigator. If radiologic PD is confirmed by the subsequent tumor imaging, the subject should be discontinued from treatment unless, in the opinion of the investigator, the subject is achieving a clinically meaningful benefit; an exception for continued treatment may be considered following consultation with the PI.

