Subjects may continue to be treated with pembrolizumab until PD is confirmed by RECIST 1.1, unacceptable adverse events (AEs), intercurrent illness that prevents further administration of treatment, investigator's decision to withdraw the subject, subject withdrawal of consent, pregnancy of the subject, noncompliance with trial treatment or procedure requirements, administrative reasons, or the subject has received 35 trial treatments (approximately 2 years) with pembrolizumab. Subjects who discontinue trial treatment for a reason other than disease progression will move into the Follow-Up Phase and should be assessed every 8 weeks ( $\pm 7$  days) by radiologic imaging to monitor disease status.

Disease status will continue to be monitored until whichever of the following occurs first: the start of new anti-cancer treatment, disease progression, death, or the end of the study. All subjects will be followed by phone contact every 12 weeks (+/- 2 weeks) for overall survival (OS) until death, withdrawal of consent from participation in the study, or the end of the study, whichever comes first.

Subjects who attain a CR by 2 tumor imaging assessments at least 4 weeks apart and who have received at least 8 treatments (approximately 6 months of therapy) with pembrolizumab may discontinue treatment at the discretion of the investigator after receiving at least 2 treatments beyond the initial determination of a CR. Subjects who stop pembrolizumab after receiving 35 trial treatments (approx. 2 years) for reasons other than PD or intolerance or who stop after attaining a CR may be eligible for retreatment with up to an additional 17 treatments (second course of treatment, approximately 1 year) after they have experienced radiographic PD after consultation with the principal investigator. The decision to retreat will be at the discretion of the investigator only if no other cancer treatment was administered since the last dose of pembrolizumab, the subject still meets the parameters listed in the inclusion and exclusion criteria, and the trial remains open.

Adverse events will be monitored throughout the trial and graded in severity according to

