### **6.5.1 When and How to Withdraw Subjects**

Subjects may withdraw consent at any time for any reason or be dropped from the trial at the discretion of the investigator should any untoward effect occur. In addition, a subject may be withdrawn by the investigator or the Sponsor if enrollment into the trial is inappropriate, the trial plan is violated, or for administrative and/or other safety reasons.

A subject must be discontinued from the trial for any of the following reasons:

- The subject or legal representative withdraws consent.
- Confirmed radiographic disease progression
  - *Note:* A subject may be granted an exception to continue on treatment with confirmed radiographic progression if clinically stable or clinically improved.
- Unacceptable adverse experiences
- Intercurrent illness that prevents further administration of treatment
- Investigator's decision to withdraw the subject
- The subject has a confirmed positive serum pregnancy test
- Noncompliance with trial treatment or procedure requirements
- The subject is lost to follow-up
- Completed 24 months of uninterrupted treatment with pembrolizumab or 35 administrations of study medication, whichever is later.
  - *Note:* 24 months of study medication is calculated from the date of first dose. Subjects who stop pembrolizumab after 24 months may be eligible for up to one year of additional study treatment if they progress after stopping study treatment after consultation with the sponsor.

- Administrative reasons

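### Section 13.5 says non-target lesions count, but 13.5.1 and 13.5.2 give them no route to confirmed progression, and 5.1 does not say which criteria govern treatment after first PD

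*Combined protocol and SAP*

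**What the plan says.** Section 13.5 lets subjects stay on treatment after first RECIST 1.1 progression under immune-related criteria, with a repeat scan 4 weeks later. If progression is confirmed the subject stops; if not, treatment resumes or continues. On what counts as a change it says: "In determining whether the tumor burden has increased or decreased, investigators should consider all target lesions as well as non-target lesions".

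The two subsections that make this operational leave non-target lesions out:

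- 13.5.1 defines tumor burden as the target diameters plus the new-lesion diameters. PD is a rise of at least 20% in that sum from its smallest value, confirmed at least 4 weeks later.
- 13.5.2 requires non-index lesions to be absent for irCR, but prints *Any* for them in the irPR, irSD and irPD rows.

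Under RECIST 1.1, 13.4.2 and Table 9 make unequivocal non-target progression PD whatever the target status. Two cautions apply: "Unequivocal progression should not normally trump target lesion status", and "In exceptional circumstances, unequivocal progression in non-target lesions may be accepted as disease progression".

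Section 5.1 points both ways. Its third paragraph says that after first PD "treatment decisions may be made by the adaptation of RECIST 1.1" set out in 13.5. Its fourth says: "Subjects may continue to be treated with pembrolizumab until PD is confirmed by RECIST 1.1". Section 6.5.1 lists "Confirmed radiographic disease progression" as a reason to discontinue, without naming the criteria.

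**The concern.** An investigator who follows the 13.5 sentence and one who follows the 13.5.1 formula and the 13.5.2 table can classify the same two scans differently. The first sees confirmed progression. The second sees stable disease, so progression is not confirmed and the instruction is to go on treating.

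The classification matters because the NOTE at the end of 13.5 attaches to confirmed progression. Its conditions (clinical stability, no further target growth, no unequivocal non-target increase, no additional new lesions) and its requirement to consult the sponsor and the DSMC are written for subjects already classed as confirmed PD. A subject classed as irSD may never reach them, even when the reason for concern is the non-target disease that the NOTE names.

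**Working it through.** No sample size, power or error rate is involved, so there is no plan figure to reproduce. The check applies the written rules to one type of case.

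**Case.** A clinically stable, re-consented subject has unequivocal progression of existing non-target lesions on two scans at least 4 weeks apart and no new lesions.

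**Assumptions.** The documents give no lesion sizes. I take a smallest sum on study equal to baseline, of 60 mm, and repeat the check with 80 mm. The irPD row of 13.5.2 appears in the text as at most a 20% increase. I read it as at least 20%, to match 13.5.1.

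**Thresholds from 13.5.1.**

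- 60 mm: PR at or below 60 × 0.70 = 42 mm; PD at or above 60 × 1.20 = 72 mm; SD between.
- 80 mm: PR at or below 80 × 0.70 = 56 mm; PD at or above 80 × 1.20 = 96 mm; SD between.

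| Smallest sum | Burden, both scans | Change | 13.5.1 | 13.5.2 | Table 9 |
|---|---|---|---|---|---|
| 60 mm | 66 mm | 66/60 = 1.100, +10.0% | SD | irSD | PD |
| 60 mm | 71 mm | 71/60 = 1.183, +18.3% | SD | irSD | PD |
| 60 mm | 72 mm | 72/60 = 1.200, +20.0% | PD | irPD | PD |
| 80 mm | 88 mm | 88/80 = 1.100, +10.0% | SD | irSD | PD |
| 80 mm | 94 mm | 94/80 = 1.175, +17.5% | SD | irSD | PD |
| 80 mm | 97 mm | 97/80 = 1.2125, +21.25% | PD | irPD | PD |

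The classifications differ whenever burden is up less than 20%, whatever the starting size. The printed sign in the irPD row does not affect the point, because the non-index entry is *Any* under either sign. Below the PR threshold the case is mostly theoretical, since 13.4.2 says non-target progression should not normally override target status.

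**Does Section 5.1 decide?** It does not. Its third paragraph permits irRECIST for treatment decisions, and its fourth names RECIST 1.1 for confirmation. Section 6.5.1 and the 13.5 NOTE refer to confirmed progression without saying by which criteria.

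**New lesions alone.** The same 5.1 conflict arises here. Take 60 mm of targets plus one 10 mm new lesion: 60 + 10 = 70 mm, and 70/60 = 1.167, or +16.7%. Table 9 calls this PD. Sections 13.5 and 13.5.1 do not.

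**The case against.** The strongest reply is that little turns on the classification. The subject is clinically stable by construction, and for such a subject 6.5.1 allows an exception after confirmed progression. Section 5.1 allows one for clinically meaningful benefit, and the 13.5 NOTE allows a narrower one. Section 1.1 permits treatment after RECIST 1.1 progression "if considered clinically appropriate by the study principal investigator". A reader might infer that the classification alone decides whether drug stops. The documents do not support that: confirmed PD makes stopping the default, and the exceptions can reverse it. This part of the reply stands.

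Second, the text leans towards stopping. Section 5.1 starts from PD by RECIST 1.1 and speaks of confirming it, so the natural reading is that the same PD is confirmed. Section 13.5.1 is headed as a target-lesion section, and 13.5.2 is a best-response table. This is fair, but 13.5 opens by letting subjects remain if they meet the immune-related criteria, 13.5.1 contains its own confirmation rule, and 13.5.2 gives the overall response. No sentence sets precedence.

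Third, the protocol names who judges. Section 13.4.2 says "the opinion of the treating physician should prevail in such circumstances", with later confirmation by the review panel or principal investigator. That settles who makes the RECIST 1.1 call, but not whether the call counts under irRECIST.

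Fourth, the last sentence of the 13.5 NOTE ends treatment beyond PD if progression worsens. It may reach a subject read as irSD, but it sits within the exception note and its scope is not stated.

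**Conclusion.** The inconsistency is real and minor. Section 13.5 says non-target lesions are to be considered. The definition and table that follow give them no way to produce confirmed irPD, and 5.1 does not say which criteria prevail.

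The consequence is limited to treatment beyond first PD: whether discontinuation is the default, and whether the NOTE's conditions and the sponsor and DSMC consultation apply. Few subjects are likely to be affected. The documents give no rate, they treat non-target-only progression as exceptional, and the clinical-stability criteria narrow the group further, so I claim no count. The millimetre examples rest on assumed sums; the 20% boundary does not.

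A reader might also infer that the efficacy results are compromised, since 13.5 has its own rule for dating progression. The documents do not support this. Section 13.5 states that irRECIST is not the primary endpoint. Section 13.6.1.1 ties PFS to first documented RECIST 1.1 progression, and ORR, DOR and DCR are also assessed by RECIST 1.1.

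**What to change.** 1. In 13.5 and 13.5.1, state that for treatment decisions PD is confirmed when either of two findings is present on the first scan and again on a scan at least 4 weeks later: (a) tumor burden (target plus new) at least 20% above the smallest sum on study; or (b) unequivocal non-target progression as defined in 13.4.2. The 4-week confirmation must apply to both limbs, as 13.5.1 already requires for burden.
2. In 13.5.2, change the non-index entry for irPR and irSD from *Any* to *No confirmed unequivocal progression*, and add an irPD row for confirmed unequivocal non-target progression. If the source document prints the irPD threshold as at most 20%, correct it to at least 20%.
3. In the fourth paragraph of 5.1, state which criteria define confirmed PD for treatment decisions.

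How to handle new lesions alone is a clinical choice for the sponsor, not a wording correction. If the 13.5 rule is chosen, keep the NOTE's conditions and the sponsor and DSMC consultation for subjects continued after RECIST 1.1 PD by new lesions. Otherwise the choice would lengthen treatment and remove a safeguard.

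The cost is wording in 13.5, 13.5.1, the 13.5.2 table and 5.1. No extra scans, data fields or patients are needed, and RECIST 1.1 remains the criterion for PFS, ORR, DOR and DCR.
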